B/ The use of the highest safely achievable proportion of 15-caliber coils, including Deltamaxx, the operator being unrestricted in the use of the coil he/she believes is appropriate at any time during the procedure using standard or adjunct techniques.

The aim of treatment is the complete angiographic exclusion of the aneurysm, or, as complete an exclusion from circulation as is feasible while minimizing risks of the procedure as per practice standards.

The interventionist and therefore the clinical and interventional research team cannot be blinded to the nature of the coils used. However, the imaging center (core lab) that will determine the success of the procedure will be blinded during its evaluation.

Although the mechanism evoked to support the potential benefit of 15-caliber coils is an increase in 'packing density', the trial does not require the use of a minimal number or length of coils of either nature, nor to reach a certain packing density. To attempt to introduce more coils, even after angiographic exclusion of the lesion, to increase packing density, could be seen as taking unjustified additional risks. The use of balloon assistance for coil deployment or stents deployed after coiling is authorized but will be recorded. Parent vessel occlusion concomitant to endosaccular coiling can be performed as long as it was not the procedure's primary intent.

Selection criteria

Inclusion criteria

- At least one ruptured or unruptured aneurysms with a dimension ≥4 mm and ≤12 mm (longest axis)
- For ruptured lesions, patients should be in WFNS grade < IV.
- The anatomy of the lesion is such that endovascular treatment is possible with both types of coils (not necessarily certain or probable)
- Patient is 18 or older
- Life expectancy is more than 2 years

Exclusion criteria

- Patients with planned treatment of an associated cerebral arteriovenous malformations
- When parent vessel occlusion, without simultaneous endosaccular coiling of the aneurysm, is the primary intent of the procedure
- Any absolute contraindication to endovascular treatment, angiography, or anaesthesia such as severe allergies to contrast or medications

Treatments

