Patients allocated to caliber-15 coiling will preferably receive caliber-15 coils (perhaps including a caliber-15 framing coil (or not), as many Deltamaxx filling coils as safely achievable, but the procedure can be completed with caliber-10 or smaller finishing coils, in order to achieve as complete an occlusion as possible, keeping the procedure as safe as possible.

Patients allocated to caliber-10 coiling will preferably receive caliber-10 coils (perhaps including a caliber-10 framing coil, caliber-10 filling and finishing coils), once more to achieve as complete an occlusion as possible, keeping the procedure as safe as possible.

Both groups will receive platinum coils only. Balloon-assisted or stent-assisted coil embolization is permitted, but should be noted in the procedure CRF.

Technical freedom

The goal of the endovascular procedure is (as usual) to realize the most complete exclusion of the lesion that is judged to be possible, while keeping risks as small as possible, using the randomization algorithm's assigned embolization material. At any time during the procedure the interventionist is unrestricted in the use any device, technique or drug judged important to the safety and success of the endovascular procedure.

If a patient is randomized to 15-caliber coils but the operator prefers, for strong clinical reasons not initially thought of at the time of recruitment, not to deploy predominantly voluminous coils in this particular case, he should proceed using appropriate coils in the best interests of the patient. The converse is also true. In any such case, the operator details reasons on the endovascular treatment case report form. Analysis will be on an intention to treat and per-protocol basis.

Randomization

DELTA is designed with 1:1 randomization.

A minimization algorithm will be used whether the aneurysm is ruptured or unruptured and previously treated or not (major recurrence).

Type, frequency and duration of follow-up

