An independent committee will adjudicate, for each patient, whether he or she has reached the endpoint. In the absence of follow-up imaging, the committee will adjudicate other potential cases of treatment failures (expected to be rare) such as:

- Hemorrhage during the follow-up period
- Retreatment of the same lesion by endovascular or surgical means during the follow-up period
- Occurrence or progression of a mass effect in relation to the treated aneurysm
- Morbidity and mortality that precludes follow-up

The pilot phase of the study was powered to detect a difference of 3% in mean packing density between the 2 groups.

Secondary outcomes:

Secondary outcomes include other indices of immediate treatment success as well as standard safety outcomes:

- Procedure-related serious adverse events
- Initial technical success of the coiling strategy
- Use of adjunct devices.
- Number and total length of coils implanted for each type
- Packing density (core-lab measured)
- Time of fluoroscopic exposure
- Immediate angiographic results according to the Montreal scale

- mRS at 1 year follow-up
- Major recurrence on follow-up angiography
- Morbidity and mortality that precludes angiographic follow-up

Concerning radiographic evidence of recurrence, the angiographers at each participating center will ensure that best projections showing residual necks at the time of treatment are repeated during follow-up evaluations. For the purpose of this study, only major recurrences or residual aneurysms that are of a size that would ideally necessitate retreatment, as judged by the core lab, will be counted. Angiographic results will also be scored according to a previously published classification system¹² as complete obliteration, residual neck or residual aneurysm and groups will be compared initially and at follow-up at 12 ± 2months.

Recurrences will be recorded (present or absent) as they are discovered, at the routine follow-up assessments as clinical symptoms appear any time during the 12 months that follow the intervention. The independent core lab will determine the presence of angiographic recurrences.

Initial technical success

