For the patients allocated to 15-caliber coils, the interventionists will have a choice to use 15-caliber coils only and/or other coils during the embolization procedure, in order to guaranty the same safety and immediate efficacy as the standard procedure. A study protocol deviation will be considered to have occurred if < 30% of coil length is 15-caliber coils. The initial technical success or failure of the procedure will be determined after treatment by the adjudication committee by reviewing core lab independent result of procedural angiogram and coils uses as recorded in the data collection sheets.

Mortality

The death rate will be recorded for the intent-to-treat analyses. It will be obtained by dividing the number of deaths by the number of patients in each group. Mortality will be categorized as being a/related to the illness, b/ related to coil embolization or c/ unrelated.

Adverse events

Adverse events will be recorded immediately after the procedure and during the 12-month follow-up period. Serious adverse events (SAEs), those that are life threatening, leading to hospitalizations or prolonged hospitalizations, as well as unexpected events will all be reported within 48 hours to the data coordination centre that will transmit the information to the DSMC. The number and severity of all reported adverse events will be recorded for each patient and for each treatment group.

Morbidity

The number and the severity of morbid events per patient will be recorded for each patient. The modified Rankin scale will be measured at follow-up appointments. This scale classifies the patients according to their neurological outcome.³⁹

Sample size

A decrease in the recurrence rate from 33 to 20% would be clinically significant. Based on Fisher's Exact test, a total sample size of 512 patients would allow detecting such a difference with a power of 90% and an alpha error of 0.05 (Table 2). A sample size of 564 patients for DELTA is sufficient to detect a decrease in the recurrence rate from 33 to 20% with an alpha error of 5% and a beta error of 10%, allowing 10% of losses at determination of the primary endpoint

Table 2: Log Rank Survival Power Analysis - Simple - Primary Hypothesis

Two Independent Proportions (Null Case) Power Analysis
Numeric Results of Tests Based on the Difference: P1 - P2
H0: P1-P2=0. H1: P1-P2=D1<>0. Test Statistic: Fisher's Exact test

	Sample	Sample	Prop H1	Prop					
	Size	Size	Grp 1 or	Grp 2 or	Diff	Diff			

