Descriptive statistics will be done on demographic variables and pre-operative and peri-operative data to compare the two groups at baseline. Means, standard deviations and range will be presented for quantitative variables and frequency tables for categorical variables. Those statistics will be broken down by treatment arm. Comparability of the groups will be assessed through independent ANOVAs (quantitative data) or Mantel-Haentzel and chi-square tests (categorical data). For the pilot phase, the number of patients with satisfactory immediate angiographic results, as well as the mean packing density, will be compared between the 2 groups. The primary outcome of the pivotal phase, recurrence rates (for both intent-to-treat end per-protocol populations) will be compared between groups through a z-test for independent proportions at 6 months and 12 months. Secondary outcomes and safety data will be compared between groups through independent t-tests (quantitative variables) or chi-square statistics (categorical data). The analyses of neurological data at follow-up will control for baseline data when possible (for tests done before discharge and at follow-up) using logistic regression, ANCOVA or Cox regression multivariate models. All tests will be interpreted with adjustment for the interim analysis to have the 0.05 level of confidence at 12 month only. Finally, a logistic regression will be used to find variables capable of predicting recurrences. The method planned is a stepwise forward with alpha < 0.05 to enter a predictor. Possible predictors include the type of the aneurysm, location, size of the aneurysm, size of the neck of the aneurysm as well as other baseline characteristics.

Pilot phase

The pivotal trial will be preceded by a pilot phase of approximately 165 patients designed to verify the feasibility of the coiling strategy, compliance to treatment group allocation, the safety of an 15-caliber platinum coil embolization strategy, recruitment rates, and the capacity to improve packing density with a standardized effect size (E/S) of 0.60, with a power of 95% and a two-sided alpha error of 0.05 (assuming the packing density of the control group will be approximately 25%). The data will be reviewed and analyzed by the DSMC and recommendations will be forwarded to the Steering Committee regarding continuation into the pivotal phase of the study.

Protection against bias

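### Does the missing criterion for initial technical success make its comparison between arms unfair to the 15-caliber group?

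*Combined protocol and SAP*

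**What the plan says.** - **Status of the outcome.** Section 2, Secondary outcomes, lists "Initial technical success of the coiling strategy" and, as a separate item, "Immediate angiographic results according to the Montreal scale". The number and total length of coils of each type is a further item in the same list.
- **Who decides.** Under Initial technical success, the verdict is binary and is reached "by the adjudication committee by reviewing core lab independent result of procedural angiogram and coils uses as recorded in the data collection sheets".
- **The threshold.** The same paragraph opens with patients allocated to 15-caliber coils and states: "A study protocol deviation will be considered to have occurred if < 30% of coil length is 15-caliber coils".
- **The other arm.** Section 2, Treatments, gives the 10-caliber arm only a preference for 10-caliber coils. Technical freedom lets an operator depart from allocation in the 15-caliber arm, adds "The converse is also true", and has the reasons recorded.
- **Analysis.** Planned analyses states: "Secondary outcomes and safety data will be compared between groups through independent t-tests (quantitative variables) or chi-square statistics (categorical data").
- **Pilot.** Section 2, Pilot phase, describes the pilot as "designed to verify the feasibility of the coiling strategy, compliance to treatment group allocation", among other aims.

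**The concern.** A binary outcome that is to be tested between arms needs a rule, and none is written. Section 3, Day to day management, sends the clinical adjudication committee to Appendix 3 for outcome definitions. Appendix 3 covers the primary outcome, packing density, safety endpoints, adverse events and end of study, but not technical success.

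Coil use is what this outcome adds to the immediate angiographic result, and the only number attached to coil use belongs to one arm. A reader may infer that a patient under 30% is a technical failure in the 15-caliber arm while no equivalent failure exists in the 10-caliber arm. The outcome would then mix procedural success with compliance in one arm only. The 15-caliber arm could show a deficit that reflects nothing but operator choices the protocol allows. The pilot treats feasibility and compliance as separate aims, and the DSMC advises on continuation from pilot data, so a mixed measure could blur that advice.

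Two smaller points add to the impression. Interventions says that "the imaging center (core lab) that will determine the success of the procedure will be blinded during its evaluation", whereas the technical success paragraph gives the verdict to the adjudication committee. Appendix 3 ends the study for patients in whom no coils are deployed, without saying whether they are technical failures.

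**Working it through.** The plan gives no rate, power or sample size for technical success, so there is no figure to reproduce. The check is textual, followed by an illustration of what one reading would imply.

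**1. Is there a criterion?** None appears in the Protocol Summary, in Section 2 or in Appendix 3. Appendices 1 and 2 could not be read. Their titles (referral centre details, investigator agreement) make a definition there unlikely.

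**2. Readings the text allows.**
- (a) Coil use informs the committee, but the 30% rule marks a deviation only.
- (b) Falling under 30% is a technical failure, in the 15-caliber arm only.
- (c) Coil use is weighed by the same judgement in both arms.

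The text labels the 30% rule a deviation and never a failure, so (b) must be added by the reader. The sentence naming coil use as review material refers to the procedure and to no arm, which fits (a) or (c).

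**3. What reading (b) would do.** Inputs from the documents: a pilot of about 165 patients at 1:1, taken as 83 in the 10-caliber arm and 82 in the 15-caliber arm, and 282 per arm in the full trial. Assumed, not in the documents: angiographic success s of 80% to 95%, equal in both arms, and a share d of 5% to 15% of the 15-caliber arm under 30%, independent of the angiogram.

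Success is s in the 10-caliber arm and s(1 − d) in the 15-caliber arm. The difference is s − s(1 − d) = s·d.

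The last two columns give the exact probability that the two-sided chi-square test without continuity correction reaches p<0.05:

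| s | d | s·d (points) | Pilot | 282 per arm |
|---|---|---|---|---|
| 0.80 | 0.05 | 4.0 | 9.7% | 21.0% |
| 0.90 | 0.10 | 9.0 | 37.7% | 86.6% |
| 0.95 | 0.15 | 14.25 | 82.9% | >99% |

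With d = 0, which is reading (a), the probability is 4.6% to 5.1%. Swapping the 83 and 82 moves the pilot figures by at most about 1 point.

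**4. How far this rests on independence.** Let o be the fraction of under-threshold patients who also fail on the angiogram. The difference is then d(1 − o). Independence means o = 1 − s. In the middle row that is o = 0.10, giving 0.10 × 0.90 = 0.09. With full overlap, o = 1, it is 0.10 × 0 = 0, and the rejection rate returns to about 5%. Difficult aneurysms could plausibly produce both fewer 15-caliber coils and incomplete occlusion, so overlap above the independent value is credible.

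**5. Reading (c).** If the same share fails on coil use in both arms, the middle case is 0.90 × 0.90 = 0.81 in each, a difference of 0.

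**6. Does a named pilot comparison use the outcome?** Planned analyses names two for the pilot: satisfactory immediate angiographic results and mean packing density. Technical success is not among them. The general sentence on secondary outcomes follows the pivotal primary analysis. No continuation rule refers to technical success.

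**The case for a change.** The strongest case for a change is that the threshold directly precedes the sentence making coil use an input, so the document invites the question whether one feeds the other and does not answer it. The Montreal grading cannot serve as the definition by itself, because it is already a separate outcome and reviewing coil use would then have no purpose. The idea in Technical freedom of predominantly using the allocated coils works in both directions, but it governs the recording of reasons and is not a success criterion. A clarification would need wording only, since the coil data are already collected.

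What stands is that the criterion is unwritten, that the bearing of the 30% rule on the verdict is unstated, and that the classification of no-coil procedures is open.

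What does not stand is the step from an unwritten rule to an unequal one. The one-sided threshold has an ordinary explanation. The 15-caliber strategy is mixed by design and may be finished with smaller coils, so a minimum share is needed to say when it was followed, for instance for the per-protocol analyses. The 10-caliber arm is simply coiled with 10-caliber coils. The remark about the core lab in Interventions is a general one, and Section 3 narrows it to angiographic success, so the two do not conflict. The no-coil line is an end-of-study rule, not an outcome rule.

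Removing coil use would also have a cost. The outcome is named for the coiling strategy, and without coil use it would largely duplicate the immediate angiographic result. Statisticians could reasonably differ on that choice.

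**Conclusion.** The gap is real, but it is one that adjudicators and analysts fill sensibly: judge both arms by one standard, and treat the 30% rule as the compliance measure the protocol says it is. On that footing the true difference from coil use is zero and the test keeps its level of about 5%.

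The 4.0 to 14.25 point deficits, and rejection probabilities up to 82.9% at pilot size and over 99% at 282 per arm, apply only if three assumptions hold together: the assumed rates, independence from the angiogram, and a failure rule the documents do not state. They illustrate a hypothetical and do not measure bias in the plan.

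The stake is one of ten unranked secondary outcomes, whose components are also reported separately. The primary endpoint, its blinded reading and the named pilot comparisons are unaffected. No change to the plan is called for.

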Mission Statement

The DELTA trial is a large multicentre prospective randomized trial of endovascular management of aneurysms comparing voluminous coils to standard, commercially available platinum coils. It aims to recruit 564 patients with ruptured or unruptured small and medium sized aneurysms (≥ 4 and ≤ 12 mm). The clinical impact will be of major significance if substantial differences are found in the outcome according to a randomized procedure.

SECTION 2: THE PROPOSED TRIAL

Design

Delta is an investigator-initiated multicenter randomized, single-blind controlled trial comparing 15-caliber coils to standard 10-caliber coils in patients harboring small to medium size aneurysms. All patients with aneurysm ≥ 4 and ≤ 12 mm or with a recurrence will be eligible. Adjudication of angiographic results will be done by a committee blinded to treatment allocation in an independent core laboratory. The study will be conducted in 10-25 centers. The study aims to enroll 564 patients equally divided between the two groups (15-caliber platinum coils vs. standard 10-caliber platinum coils), to obtain statistical significance in the primary endpoint, the occurrence of a recurrence at follow-up. The forecast duration of the study will be 6 years, the first 4 years for patient recruitment and accrual plus 12 months of follow-up.

The pivotal trial will be preceded by a pilot phase of approximately 165 patients, over approximately 3 years, designed to confirm the feasibility of the coiling strategy, its safety, the enrolment rates, as well as to compare packing densities between the 2 groups.

Hypotheses

The use of 15-caliber platinum coils will lead to a decrease in the number of patients that reach the primary endpoint from 33 to 20% at 12 ± 2 months.

The pilot phase has been powered to test the hypothesis that the use of 15-caliber platinum coils will lead to an increased packing density as compared to caliber 10 coils from an expected mean of 25% to 28% (95% power; alpha 0.05).

Interventions

The goal of the study is to assess if the use of voluminous 15-caliber coils could reduce the number of patients reaching the primary endpoint with little if any additional risk compared to standard caliber 10 commercially available platinum coils. Thus the interventions will consist of either:

A/ Standard, commercially available 10-caliber coil embolization of aneurysms, using standard or adjunct techniques.

Or

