APPENDIX 3: ADJUDICATION OF OUTCOMES

Primary outcome:

An independent Committee will adjudicate, for each patient, whether he or she has reached the endpoint. In the absence of follow-up imaging, the committee will adjudicate other potential cases of treatment failures (expected to be rare) such as:

- Hemorrhage during the follow-up period
- Retreatment of the same lesion by endovascular or surgical means during the follow-up period
- Occurrence or progression of a mass effect in relation to the treated aneurysm
- Morbidity and mortality that precludes follow-up

The pilot phase of the study was powered to detect a difference of 3% in mean packing density between the 2 groups. This will be measured by the Core lab. For both types of treatment, the packing density (PD) will be calculated as the volume of coils (VC) over the volume of the aneurysm (VA): PD = VC/VA with VA = $(4/3)\pi(length/2)(width/2)^2$

Safety

A. Safety data

Safety endpoints

- Mortality
- Morbidity (mRS ≥ 3)
- Combined Mortality & Morbidity(M&M) (mRS ≥ 3 at 12 months)
- Serious Adverse Event

Endpoint assessment

- For all DELTA patients
- Separately for ruptured and unruptured DELTA patients

Causality attribution

- Treatment-related
- Strictly treatment related: any M&M associated with a procedural event or complication or hemorrage
- Possibly related: any M&M occurring within 30 days
- Not treatment related (> 30 days)
- Related to aneurysm
- Unrelated

Safety data will be adjudicated by an independent committee.

Example of a table supplied to the DSMC: Mortality and Morbidity (mRS \geq 3) All patients Group B Group A **DELTA** ruptured DELTA unruptured Treatment-related (within 30 days) Strictly Possibly Aneurysm-related (> 30 days) Not related (> 30 days) This pattern will apply to mortality, morbidity, morbi-mortality and SAEs. **B.** Definitions **Adverse Event** Any procedural event (thromboembolic, hemorrhage, complication). During follow-up, any symptomatic event. During follow-up, any imaging finding secondary to investigation of symptom. Adverse Events will be categorized into: minor or moderate and serious **Serious Adverse Event** Results in death or is life threatening. Requires hospitalisation or prolongation of existing hospitalisation. Results in persistent or significant disability or incapacity or is otherwise considered medically significant by the investigator **End of study** Death

- No coils deployed during procedure or additional procedure

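### Adjusting packing density, coil number and coil length for aneurysm volume would add precision at almost no cost; the planned unadjusted comparisons remain valid

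*Combined protocol and SAP*

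**What the plan says.** Packing density is the outcome on which the pilot is sized. Section 2, Hypotheses, expects the mean to rise "from an expected mean of 25% to 28% (95% power; alpha 0.05"), and the Pilot phase paragraph states the same target "with a standardized effect size (E/S) of 0.60, with a power of 95% and a two-sided alpha error of 0.05".

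On analysis, Section 2, Planned analyses, says only that the number of satisfactory immediate angiographic results, "as well as the mean packing density, will be compared between the 2 groups". The general rule in the same paragraph for quantitative secondary outcomes, a list that includes packing density and the number and total length of coils, is the independent t-test. Baseline adjustment is planned only for neurological data at follow-up. Aneurysm size appears there only as a candidate predictor in the stepwise model for recurrence.

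Appendix 3 defines the outcome: "the packing density (PD) will be calculated as the volume of coils (VC) over the volume of the aneurysm (VA"), with the aneurysm volume computed as an ellipsoid from length and width and the measurement made by the core lab. Eligibility covers a longest axis of 4 to 12 mm. The minimization in Section 2, Randomization, uses rupture status and previous treatment, not size.

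**The concern.** A baseline quantity that may be related to the outcome is already derived for every patient with a density value, yet the analysis does not use it. Any part of the variance in packing density that aneurysm volume explains stays in the error term. For coil number and total length the link to volume is far more direct, because neither is divided by volume.

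What is at stake is the width of the confidence intervals in the pilot report. Packing density is one of several inputs to the Data Safety and Monitoring Committee's recommendation on continuing to the pivotal phase.

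**Working it through.** **Inputs from the protocol.** Means of 25% and 28%; effect size 0.60; power 95%; two-sided alpha 0.05; 1:1 allocation; about 165 patients; longest axis 4 to 12 mm.

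**Assumptions.** A 10% loss in the pilot (the protocol states this allowance only for the pivotal phase); R² of packing density on log volume (not in the documents, so shown as a range); spherical aneurysms; caliber read as thousandths of an inch.

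**Reproducing the pilot size.** The implied SD is 3 / 0.60 = 5 points. A two-sample t-test (noncentral t) needs 74 per arm, or 148 in all, for 95.2% power. With 10% loss, 148 / 0.9 = 164.4, rounded up to 165, which matches "The pivotal trial will be preceded by a pilot phase of approximately 165 patients". So 165 fits an unadjusted comparison. If nobody were lost, 82 per arm would give about 97% power.

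**Packing density with one covariate.** The residual SD is 5 × √(1 − R²) and the standard error is that value × √(2/74). The noncentrality for a true difference Δ is Δ / SE. Degrees of freedom are 146 without the covariate and 145 with it.

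| Assumed R² | SE (points) | Fall in SE | Power, true difference 3 | Power, true difference 2 |
|---|---|---|---|---|
| 0 | 0.82 | 0% | 95.2% | 68% |
| 0.02 | 0.81 | 1% | 95.6% | 68% |
| 0.10 | 0.78 | 5% | 96.9% | 72% |
| 0.30 | 0.69 | 16% | 99.1% | 82% |

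The price is one degree of freedom. Adjustment breaks even at an R² of about 0.7%; below that, the loss is too small to show in the table.

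**Coil length.** A sphere of diameter D has volume πD³/6: 33.5 mm³ at 4 mm and 904.8 mm³ at 12 mm, a ratio of (12/4)³ = 27. A 0.010-inch coil has radius 0.127 mm and cross-section π × 0.127² = 0.05067 mm². Length at 25% density is 0.25 × volume / cross-section:

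- 4 mm: 0.25 × 33.5 / 0.05067 = 165 mm, about 17 cm.
- 12 mm: 0.25 × 904.8 / 0.05067 = 4,464 mm, about 446 cm.

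In a simulation with diameters uniform over 4 to 12 mm, spheres, one coil caliber and density 25% with SD 5 points, volume explained about 90% of the variance in length, and log volume about 95% of the variance in log length. On the log scale, the adjusted SE would be about √(1 − 0.95) = 0.22 of the unadjusted one. The distribution of diameters is assumed, and mixed calibers within a procedure would weaken the fit, so this shows the order of magnitude only.

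**The case against.** The strongest reply is that packing density is already coil volume divided by aneurysm volume. A 27-fold range in the denominator is therefore not a 27-fold source of variance in the outcome, because operators fill to the sac. Only a remaining trend of mean density with volume would be removed by ANCOVA, and the documents give no evidence on whether such a trend exists. If size affects only the scatter of density and not its mean, the covariate gains nothing. All of this stands, and it is why the table starts at R² = 0.

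A reader might also infer that leaving out size makes the pilot underpowered. The documents do not support this. The SD of 5 implied by the effect size is the total SD of the outcome, so it already contains whatever variation size contributes, and power is about 95% without adjustment. Whether 5 is the right SD is a separate question.

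Nor does the absence of size from the minimization bias the comparison. Randomization keeps the t-test valid, and its standard error already allows for chance imbalance in size. Baseline comparisons between groups are planned, so a marked imbalance would probably be noticed, though the plan does not say it would be adjusted for.

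The decision consequence is limited too. The continuation recommendation also rests on feasibility, compliance, safety and recruitment, and the plan sets no significance rule for density.

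Finally, Appendix 3 does not say when aneurysm volume is measured. The treatment plan in Section 4 has pre-treatment images sent to the coordinating centre, so a baseline measurement is plausible, but it is an inference.

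**Conclusion.** This is a precision improvement, not an error or a bias. The planned comparison of mean packing density is valid and reaches its stated power on the plan's own inputs, taking 10% loss as an assumption.

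For density, the gain from adjustment ranges from nothing to a 16% smaller standard error over an assumed R² of 0 to 0.30. At the 3-point target this moves power from 95.2% to at most 99.1%. It would matter more if the true difference were 2 points: power would be 68% unadjusted and 72% to 82% at an R² of 0.10 to 0.30. The documents do not say where in this range the trial lies.

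For total coil length the case is stronger. The length needed differs 27-fold between the smallest and largest eligible spheres at equal density, so an unadjusted t-test would be inefficient. Coil number should also depend on volume, though its gain was not computed. Neither is the outcome on which the pilot is sized.

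**What to change.** Amend Section 2, Planned analyses, before any arm-level pilot data are seen, so that the choice of covariate cannot look data-driven:

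- Compare pilot packing density by ANCOVA on allocated arm, with log aneurysm volume as a pre-specified covariate. Report the adjusted difference with its 95% CI, and the unadjusted difference as a sensitivity analysis.
- State that the volume is the core lab's measurement from pre-treatment images, so that it is a baseline value that allocation cannot affect.
- Analyse coil number and total coil length with the same covariate, taking length on the log scale. Say how patients with no coil deployed are handled, since Appendix 3 foresees such cases and their log length is undefined.

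The cost is a few sentences in the analysis plan and one degree of freedom per model. No new measurement is needed, provided the core lab derives the volume from the pre-treatment images.
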